**Statistical Analysis Plan**  
CX-4945 for Community-Acquired Pneumonia

---

Visit Name	Visit Day	Acceptable visit window
	-2 ~ 1 (else)	
Visit 2 (Day 1)	1	NA
Visit 3 (Day 5/7)	$5 \pm 1$ (v1.0) $7 \pm 1$ (else)	Day 4~10
Visit 4 (Day 15)	$15 \pm 2$	Day 11~20
Visit 5 (Day 29)	$29 \pm 3$	Day 21~40

### **3.2.11 SENSITIVITY ANALYSES**

For primary efficacy endpoint and secondary points that is the percentage of subjects with all cause hospitalization, emergency room visit or death during study period, event rate including ‘Treatment Fail’ rate will be tested.

For time to symptom resolution for fever and subjects without symptom resolution for fever, censoring at (1) the last temperature measurement time point of the subject, (2) the last temperature measurement time point of all subjects, will both be derived for analysis.

For by-visit efficacy endpoints, ITT analyses applying LOCF (Last Observation Carry Forward) will be performed.

### **3.2.12 SUBGROUP ANALYSES**

Domain includes SARS-CoV-2 Domain and Influenza Virus Domain. By-domain subgroup analysis will be performed. Other subgroup analyses which are conditioned to the test are mentioned in section 3.2.4 and 3.2.6.

### **3.2.13 AD HOC ANALYSIS**

An ad hoc exploratory subgroup analysis will be conducted in this study. The analysis will be performed separately within the HIV and Non-HIV groups to evaluate differences in inflammatory markers and cytokine between treatment arms. Additionally, the analysis will also be performed within the Asthma and Non-Asthma groups.

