## **2 STUDY DESIGN**

### **2.1 OVERALL DESIGN**

This is a Phase II, multi-center, double-blind, randomized, interventional study in approximately 120 subjects to evaluate clinical benefit of CX-4945 in adult outpatients with SARS-CoV-2 and influenza viral infection-associated pneumonia. The subjects will be recruited into two domains, including SARS-CoV-2 and Influenza virus domains. The study will compare the efficacy of SOC combined with CX-4945 against SOC paired with a placebo, utilizing a 1:1 allocation ratio in each domain. The study arms will be listed below:

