##### **3.2.2 GENERAL APPROACH**

All available data will be displayed via subject data listings, and summarized for each evaluation time point as appropriate by study domain (including domain-pooled) and study arm. The categorical data will be summarized with the number of subjects and percentage. Continuous data will be summarized by descriptive statistics (i.e., number of subjects, mean, standard deviation, minimum, maximum, and median).

In general, categorical data will be analyzed by using Fisher's exact test or Cochran-Mantel-Haenszel test stratified by domain for comparing overall treatment group difference. For by-domain subgroup analysis, categorical data will be tested by using Fisher's exact test or Chi-square test.

Continuous data will be analyzed by using analysis of variance (ANOVA) on baseline data, and by using analysis of covariance (ANCOVA) on change data for comparing overall

treatment group difference. Non-parametric method shall be adapted or log-transformation may be needed for non-normally distributed data. For by-domain subgroup analysis, baseline continuous data will be tested by using two-sample t test or Wilcoxon Rank-sum test, post-treatment continuous data will be tested by using ANCOVA or Wilcoxon Rank-sum test.

For the ANOVA and ANCOVA model, factors of treatment, domain (as appropriate), site and baseline value (for post-baseline data) and other baseline factors will be included in the model if significant, those non-statistically significant factors except treatment will be removed from the model (alpha=0.1 for interaction, 0.05 for others).

All statistical tests will be two-sided and evaluated at the 0.05 level of significance. All confidence intervals, if provided, will be the 95% CI.

The most recent value before first dose administration will be defined as the baseline value; therefore, the baseline value will be the outcome of the closest evaluation performed before or equal to the first dosing date.

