## **3.3 STATISTICAL/ANALYTICAL ISSUES**

### **3.3.1 ADJUSTMENTS FOR COVARIATES**

Due to early termination of the study, there was a small number of subjects enrolled at most sites. In addition, there was no similar site-related properties among sites. Therefore, Site is not considered as a factor in the ANOVA and ANCOVA model; only treatment, domain (as appropriate), and baseline value (for post-baseline data) are the factors in the ANOVA and ANCOVA model.

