#### **3.4.1 STATISTICAL METHODS CHANGE**

Due to early termination of the study, only 44 subjects were randomized. For both the primary and secondary endpoints, the number of events observed prior to unblinding was insufficient to support reliable estimation using logistic regression. Therefore, Logistic regression will not be applied in the analysis.

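### The HIV and asthma analyses compare arms separately within each subgroup with no treatment-by-subgroup term, so they cannot show whether the effect on markers differs between groups

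*SAP*

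**What the plan says.** SAP 3.2.13 states that "The analysis will be performed separately within the HIV and Non-HIV groups" to "evaluate differences in inflammatory markers and cytokine between treatment arms", and that "the analysis will also be performed within the Asthma and Non-Asthma groups". It calls the analysis ad hoc and exploratory. It gives no model, interaction term, minimum subgroup size or rule for reading the results.

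SAP 3.2.12 adds that "By-domain subgroup analysis will be performed". SAP 3.2.2 and 3.4.3 give the tests to be run within each domain.

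SAP 3.2.2 sets the general rule: "All statistical tests will be two-sided and evaluated at the 0.05 level of significance". It also mentions a 0.1 level for interactions in the ANOVA and ANCOVA models, without naming any interaction. SAP 3.3.1 then closes the list: "only treatment, domain (as appropriate), and baseline value (for post-baseline data) are the factors in the ANOVA and ANCOVA model". SAP 3.3.6 treats multiplicity as not applicable.

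On size, SAP 3.4.1 reports that "only 44 subjects were randomized".

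**The concern.** The natural reason to split by HIV or asthma is to see whether the drug acts differently in the two groups. The quantity that answers this is the difference between the two treatment effects, with its uncertainty. Two within-group p-values do not estimate it. Each depends on the group's size as well as on the effect, so a large group can reach 0.05 and a small one miss it when the effect is identical in both.

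At stake is a conclusion that the drug moves cytokines only in, say, patients without HIV. The primary endpoint is not touched, but such a result could steer the choice of population for a later trial.

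**Working it through.** **Inputs from the SAP.** 44 randomized (3.4.1); "utilizing a 1:1 allocation ratio in each domain" (2.1), so about 22 per arm; two-sided 0.05 (3.2.2); change-from-baseline markers and cytokines assessed at Days 7, 15 and 29 (section 1).

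**Assumptions.** The SAP gives no subgroup sizes, SDs or effects, and marker names are redacted. I take two splits of the 44: unequal (4 v 4 and 18 v 18) and equal (11 v 11 twice). True effects run from 0 to 1.0 SD and are the same in everyone. A two-sample t test stands in for ANCOVA. The plan has no subgroup power or error figure to reproduce.

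**Step 1: one marker, one visit, one split.** With powers p1 and p2 from the noncentral t distribution,

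P(exactly one significant) = p1(1 − p2) + p2(1 − p1).

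| True effect in everyone | Power 4 v 4 | Power 18 v 18 | Exactly one, unequal split | Power 11 v 11 | Exactly one, equal split |
|---|---|---|---|---|---|
| 0 | 0.050 | 0.050 | 9.5% | 0.050 | 9.5% |
| 0.5 SD | 0.092 | 0.308 | 34% | 0.201 | 32% |
| 0.8 SD | 0.160 | 0.645 | 60% | 0.431 | 49% |
| 1.0 SD | 0.223 | 0.830 | 68% | 0.607 | 48% |

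For example, at 0.8 SD with the unequal split: 0.160 × 0.355 + 0.645 × 0.840 = 0.057 + 0.542 = 0.599. Both tests are significant in 0.160 × 0.645 = 10%. For equal strata the formula is 2p(1 − p), which cannot exceed 50%.

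**Step 2: many looks, no true effect.** Over k independent looks the chance of at least one such pattern is 1 − (1 − 0.095)^k. This is 26% for k = 3, 50% for k = 7 and 83% for k = 18. Real looks share subjects and are correlated. A simulation of 44 subjects with three splits (HIV, asthma, domain) and outcome correlation 0.5 gave about 64% for 6 outcomes (for example 2 markers at 3 visits) and 84% for 12. It used 400 runs, with Monte Carlo error up to 2.5 points.

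**Step 3: by-domain binary endpoints.** Exact enumeration of Fisher's test at an assumed 11 per arm in each domain, with no effect and event rates of 5% to 30%, gives exactly one significant domain in 0.03% to 2.8% of trials. Against zero events in the other arm, 5 of 11 is the first count to reach p < 0.05 (p = 0.035).

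**Step 4: the interaction test.** By normal approximation, the standard error of the difference in effects, in SD units, is √(2/n1 + 2/n2), with n1 and n2 the numbers per arm in the two strata. For a 0.8 SD difference in effect:
- Equal split: √(2/11 + 2/11) = 0.603; 0.8/0.603 = 1.327; power = Φ(1.327 − 1.96) = 26%.
- Unequal split: √(2/4 + 2/18) = 0.782; 0.8/0.782 = 1.023; power = Φ(1.023 − 1.96) = 17%.

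Its false-positive rate stays at the nominal 5%, against the Step 1 rates for reading two p-values side by side.

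**The case against.** The strongest reply is that SAP 3.2.13 promises little. It labels the analysis ad hoc and exploratory, SAP 3.4.5 lists it among changes from the protocol, and it covers only markers and cytokines. Its stated aim is a between-arm comparison within each group, not a test of effect modification. It names no test, SAP 3.2.1 even says that there is no statistical testing, and the table shells are in separate documents. All of this stands and limits the harm. It does not remove the problem: SAP 3.2.2 sets 0.05-level tests as the general approach, nothing exempts 3.2.13, and paired subgroup results invite a comparison that they cannot support.

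A reader might also infer more than the documents allow:

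- **That a false one-group result is the likely outcome.** For a single comparison this holds only with unequal strata and a large uniform effect, about 0.7 SD or more for the 36/8 split. It is 9.5% with no effect and never above 50% with equal strata. The documents give neither the sizes nor the effects.
- **That the by-domain analyses, including the primary endpoint, carry the same risk.** Step 3 shows that Fisher's test at this size rarely gives a one-domain result under no effect. Domain is also a randomization stratum with a planned minimum size (SAP 2.2 and 2.3), unlike the late HIV and asthma splits.
- **That the SAP rules out interactions altogether.** SAP 3.2.2 keeps a level for them, while 3.3.1 lists only main factors and explains why site was dropped. For domain, the two sections are unclear when read together.

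The low power of the interaction test is a fair objection too. It is a reason to put the weight on the estimate and its interval.

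**Conclusion.** The concern holds for the HIV and asthma splits, and for by-domain analyses of continuous endpoints. As written, the plan leads to within-subgroup p-values that cannot show a differential effect, and it specifies no treatment-by-subgroup term for the HIV and asthma splits. A misleading one-group pattern has a chance per comparison between 9.5% (no effect) and 68% (1.0 SD, unequal split), and the chance of at least one grows over markers, visits and splits. These figures rest on assumed subgroup sizes, a uniform effect and t-test power in place of ANCOVA. Because the analysis is labelled exploratory and does not affect the primary endpoint, this is a correction that should be made, not a threat to the trial's main result.

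**What to change.** - In SAP 3.2.13, fit one ANCOVA per marker to all ITT subjects with treatment, domain, baseline, subgroup (HIV, then asthma in its own model) and treatment-by-subgroup.
- Report the number per arm in each stratum, each stratum's treatment difference with 95% CI, and the interaction estimate with 95% CI. Drop the within-stratum p-values and label the results exploratory.
- Use treatment-by-domain in the same way for continuous by-domain endpoints only.
- Reconcile the interaction level in SAP 3.2.2 with the factor list in 3.3.1, naming the interactions to be fitted. State in 3.2.1 how its no-testing sentence fits with 3.2.2.

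The documents give no basis for a fixed minimum subgroup size, so showing the stratum sizes and interval widths is enough. The cost is SAP wording and one simple model per marker and split, with no new data. The downside is the low power in Step 4: with 44 subjects the analysis can neither establish nor exclude a difference in effect, and the report should say so.

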## **3.3 STATISTICAL/ANALYTICAL ISSUES**

### **3.3.1 ADJUSTMENTS FOR COVARIATES**

Due to early termination of the study, there was a small number of subjects enrolled at most sites. In addition, there was no similar site-related properties among sites. Therefore, Site is not considered as a factor in the ANOVA and ANCOVA model; only treatment, domain (as appropriate), and baseline value (for post-baseline data) are the factors in the ANOVA and ANCOVA model.

### **3.3.2 HANDLING OF DROPOUTS OR MISSING DATA**

For primary efficacy endpoint and secondary points that is the percentage of subjects with all cause hospitalization, emergency room visit or death during study period, the subject will be counted as ‘Treatment Fail’ when subject has been terminated the study and event observation has been stopped before Day 29 with no event observed.

For by-visit efficacy endpoints, ITT analyses applying LOCF (Last Observation Carry Forward) data imputation will be performed additionally as a sensitivity analysis.

### **3.3.3 HANDLING OF PROTOCOL DEVIATIONS**

Protocol deviations, including operational and non-operational deviations, will be verified and logged according to SOP. Major DVs of this study, including the items below but not limited to, will be justified by the BSS upon the confirmation of sponsor. Relevant statistics are displayed in Tables 14.1.3.

- Violation of inclusion/exclusion criteria (wrong subject entry)
- Administration of prohibited therapy (medication / procedure / surgery)
- Non-compliant with the key study procedures
- Measurement/visit out of scheduled time window that may have significant impact on key efficacy / safety data
- Low treatment compliance / exposure
- Study was not withdrawn according to study withdrawal criteria

### **3.3.4 INTERIM ANALYSIS AND DATA MONITORING**

There is no planned interim analysis in this study.

### **3.3.5 MULTICENTER STUDIES**

This is a multi-center study. Data from all sites will be pooled for analysis.

### **3.3.6 MULTIPLE COMPARISON/MULTIPLICITY**

Not applicable.

### **3.3.7 USE OF AN “EFFICACY SUBSET” OF SUBJECTS**

In addition to ITT population, efficacy data will be analyzed in PP and mPP population.

### **3.3.8 ACTIVE-CONTROL STUDIES INTENDED TO SHOW EQUIVALENCE**

Not applicable.

### **3.3.9 DRUG DOSE, DRUG CONCENTRATION, AND RELATIONSHIPS TO RESPONSE**

Not applicable.

### **3.3.10 DRUG AND DRUG DISEASE INTERACTIONS**

Not planned in this study.

### **3.3.11 BY SUBJECT DISPLAY**

Individual subject data will be listed by measure and time point.

By-subject data are displayed in **Appendix 16.2**.

### **3.4 CHANGES FROM PROTOCOL-PLANNED ANALYSES**

All the eligibility criteria will follow the latest version of study protocol. Visit Adjustment is defined in section 3.2.8.

#### **3.4.1 STATISTICAL METHODS CHANGE**

Due to early termination of the study, only 44 subjects were randomized. For both the primary and secondary endpoints, the number of events observed prior to unblinding was insufficient to support reliable estimation using logistic regression. Therefore, Logistic regression will not be applied in the analysis.

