7.3. General Consideration

Statistical analyses will be performed using SAS® for Windows, version 9.4 or later. All available data will be displayed via subject data listings, and summarized for each evaluation time point as appropriate by study domain (including domain-pooled) and study arm. The categorical data will be summarized with the number of subjects and percentage. Continuous data will be summarized by descriptive statistics (i.e., number of subjects, mean, standard deviation, minimum, maximum, and median). For by visit (by Day) analyses, the acceptable window for each visit will be defined in the Statistical Analysis Plan (SAP).

In general, categorical data will be analyzed by using Logistic regression (on efficacy data), Fisher's exact test or Cochran-Mantel-Haenszel test stratified by domain for comparing overall treatment group difference (treatment odds ratio for Logistic regression). For by-domain subgroup analysis on efficacy data, categorical data will be tested by using Fisher's exact test or Chi-square test.

Continuous data will be analyzed by using analysis of variance (ANOVA) on baseline data, and by using analysis of covariance (ANCOVA) on change data for comparing overall treatment group difference. Non-parametric method shall be adapted or log-transformation may be needed for non-normally distributed data. For by-domain subgroup analysis on efficacy data, continuous data will be tested by using two-sample t test or Wilcoxon Rank-sum test.

For the ANOVA, ANCOVA model and Logistic regression, factors of treatment, domain (as appropriate), site and baseline value (for post-baseline data) and other baseline factors (for post-baseline efficacy data, to be defined in the SAP, as appropriate) will be included in the model if significant, those non-statistically significant factors except treatment will be removed from the model (alpha=0.1 for interaction, 0.05 for others). The Logistic regression result will be presented with treatment odds ratio and its 95% confidence interval (CI).

All statistical tests will be two-sided and evaluated at the 0.05 level of significance. All confidence intervals, if provided, will be the 95% CI.

The most recent value before first dose administration will be defined as the baseline value; therefore, the baseline value will be the outcome of the closest evaluation performed before or equal to the first dosing date.

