## **2.2 RANDOMIZATION AND BLINDING**

The study treatment will be randomly assigned to subjects. The randomized sequence of study treatments will be generated by a qualified biostatistician. The randomization schedule will be kept and maintained by the designated personnel before the study begins and until the database lock. The biostatistician prepares the schedule with a 1:1 randomization ratio (CX-4945: Placebo) by stratified randomization with study domains and study sites strata. Also, block permutation is used for generating randomization schedule.

This is a double-blind study. Neither the subject nor the investigators, clinic administrators, or sponsor staff who involve in the treatment or clinical evaluation of the subjects will be aware of the treatment received either at the time of randomization or later, throughout the conduct of the trial. Assigned unblinded team may include study site staff, CRO's personnel and/or Senhwa Biosciences, Inc's personnel. Other personnels involved in the study (the investigator and the clinical monitor) will be blinded until the database lock.

The treatment codes will not be prematurely broken unless an emergency situation, when the appropriate management of the subject necessitated acknowledgement of the treatment allocation, occurred. In the event of a medical emergency, if possible, the medical monitor should be contacted first to discuss the need for unblinding. For unblinding a subject, the treatment code blind can be obtained by the investigator, by accessing the EDC system.

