## **2.3 SAMPLE SIZE DETERMINATION**

To ensure 120 evaluable participants and accounting for a 10% attrition rate, approximately 136 subjects will be enrolled for the study. Note that the sample size for this exploratory study is not determined by statistical power considerations, but is considered adequate for the preliminary

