**The percentage of subjects exhibiting disease progression / health improvement in health status**

NIAID score and changes in NIAID score will be tabulated descriptively by visit. For protocol version 1.0, 6-Point Ordinal Scale collected for subjects of Influenza Virus domain will be converted to corresponding NIAID score (*refer to [Instructions and Abbreviations] of Subject Data Listings Specification for NIAID 6-point Score Conversion to 8-point Score*) and combined with NIAID score for analyses.

The percentage of subjects with increasing NIAID score (exhibiting disease progression) and with decreasing NIAID score (exhibiting health improvement) will be presented with the corresponding Clopper-Pearson exact 95% CI, and tested by using Fisher's exact test or Cochran-Mantel-Haenszel test, respectively.

**The percentage of subjects with a negative RT-PCR result for the SARS-CoV-2 (only for SARS-CoV-2 domain) or the influenza virus (only for influenza virus domain) on Day 7**

The percentage of subjects with RT-PCR negative results will be tested between treatments by using Chi-square test or Fisher's Exact test.

FilmArray data (Negative/Positive) obtained from Protocol v.1.0 will be integrated into and considered equivalent to the results for RT-PCR.

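### X-ray, NIAID, RT-PCR and CRP responder endpoints have no planned interval on the treatment effect, and with 44 subjects their tests alone say little

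*SAP*

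**What the plan says.** **General rule.** Protocol 7.3 offers logistic regression, Fisher's exact test or the Cochran-Mantel-Haenszel (CMH) test for categorical efficacy data. It ties an effect measure to the first of these: "The Logistic regression result will be presented with treatment odds ratio and its 95% confidence interval (CI").

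**Endpoint rules in the protocol.** Section 7.7.1 assigns logistic regression to the primary endpoint, and 7.7.2 carries it to the all-cause composite by reference. For X-ray, NIAID and RT-PCR (7.7.2) and CRP normalization (7.7.3) only tests are named. All but RT-PCR also get a Clopper-Pearson CI.

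**SAP.** Section 3.4.1 reports that "only 44 subjects were randomized" and that events seen before unblinding were too few for a reliable model, and concludes: "Therefore, Logistic regression will not be applied in the analysis". Section 3.2.2 then lists only Fisher, CMH or Chi-square tests for categorical data. What remains is:

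| Endpoint | Per-arm 95% CI | Test | Difference with 95% CI |
|---|---|---|---|
| Primary composite (3.2.3) | yes | yes | yes, normal approximation |
| All-cause composite (3.2.4) | yes | yes | yes, as primary |
| X-ray improved or normal (3.2.4) | yes | yes | no |
| NIAID progression; improvement (3.2.4) | yes | yes | no |
| RT-PCR negative, Day 7 (3.2.4) | no | yes | no |
| CRP normalized, Day 7 (3.2.6) | yes | yes | no |

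For RT-PCR the whole instruction is that the percentage "will be tested between treatments by using Chi-square test or" Fisher's exact test.

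**The concern.** SAP 2.3 describes an exploratory trial whose "sample size for this exploratory study is not determined by statistical power considerations". SAP 3.2.1 even says that no statistical testing is done, although 3.2.2 states: "All statistical tests will be two-sided and evaluated at the 0.05 level of significance". The useful product of such a trial is an estimate of the effect with its uncertainty, from which a later study can be planned. For five responder endpoints (X-ray, NIAID progression, NIAID improvement, RT-PCR, CRP) the only planned between-arm result is a p-value, and at this sample size it will usually be non-significant whether or not the drug does something worthwhile. The SAP already accepts the need for a difference with its CI for the two composites, and nothing in it explains why the other responder endpoints are treated differently.

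**Working it through.** **Inputs from the documents.** 44 randomized (SAP 3.4.1). Allocation: "The biostatistician prepares the schedule with a 1:1 randomization ratio (CX-4945: Placebo) by stratified randomization with study domains and study sites strata" (SAP 2.2). Two-sided 0.05 tests and 95% CIs (SAP 3.2.2).

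**Assumptions.** 22 per arm, from 44/2; no per-arm count is given. About 11 per arm within a domain, from 22/2; the domain split is not given. Response counts and rates are illustrative, because the documents state none. All intervals below are unstratified, because no counts by domain are available.

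**The plan's own figure.** "To ensure 120 evaluable participants and accounting for a 10% attrition rate, approximately 136 subjects will be enrolled for the study" (SAP 2.3). Overall, 120/0.9 = 133.3, rounded up to 134. If the 120 are spread evenly over four arms, 30/0.9 = 33.3, rounded up to 34, and 4 × 34 = 136. The figure reproduces. The trial reached 44/136 = 32% of it.

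**Power of the planned test.** Exact power of Fisher's test, summing the binomial probabilities of all outcomes with p ≤ 0.05:

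| True rates | Per arm | Power |
|---|---|---|
| 70% v 50% | 22 | 17.5% |
| 90% v 70% | 22 | 28% |
| 80% v 50% | 22 | 43% |
| 90% v 50% | 22 | 79% |
| 80% v 50% | 11 | 17% |

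A non-significant result is therefore more likely than not even for a true 30-point effect from 50%.

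**Interval on the difference.** Newcombe's method takes the Wilson limits (l, u) of each arm and sets

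- lower = d − √[(p1 − l1)² + (u2 − p2)²]
- upper = d + √[(u1 − p1)² + (p2 − l2)²]

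*14/22 v 14/22.* p = 63.6% in each arm, Wilson limits 43.0% to 80.3%. The half-width is √(20.7² + 16.6²) = 26.5 points, so d = 0 with 95% CI −26.5 to +26.5. The planned output would be 41% to 83% (Clopper-Pearson) in each arm and p = 1.0.

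*15/22 v 9/22.* p1 = 68.2% (Wilson 47.3 to 83.6), p2 = 40.9% (23.3 to 61.3), d = 27.3 points.
- Lower: 27.3 − √(20.9² + 20.4²) = 27.3 − 29.2 = −1.9.
- Upper: 27.3 + √(15.5² + 17.7²) = 27.3 + 23.5 = +50.7 (from unrounded values).

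The planned output would be 45% to 86%, 21% to 64%, and Fisher p = 0.13.

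*6/11 v 6/11, one domain.* p = 1.0, with 95% CI −36 to +36 points.

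**Sparse cells.** With 0/22 v 2/22 Newcombe still gives −9 points (−28 to +7). With 0/22 v 0/22 the normal approximation used for the primary endpoint collapses to 0 to 0, while Newcombe gives −15 to +15. Too few events rules out a logistic model but not a score-based interval.

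**The case against.** **The removal of logistic regression is not the sole cause.** A reader might infer that SAP 3.4.1 took away estimates these endpoints had been promised. The documents do not support that. Protocol 7.3 gave logistic regression as one option among three, and Protocol 7.7.2 and 7.7.3 already listed only tests here. SAP 3.2.4 and 3.2.6 largely repeat that text. The gap predates the SAP, and 3.4.1 removed only the general route that might have filled it. This objection stands in full.

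**The imprecision is not hidden for most of these endpoints.** It is tempting to say that a null result could not be told from an uninformative one. For X-ray, NIAID and CRP that goes too far: 41% to 83% in both arms beside p = 1.0 plainly shows how little is known. SAP 3.2.2 also requires counts and percentages for all categorical data, so a reader can compute an unstratified difference, even for RT-PCR. This stands in part. Two per-arm intervals are not an interval on the effect, a domain-stratified estimate cannot be recovered from pooled counts, and RT-PCR has no planned interval.

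**Fever resolution is a different matter.** It was always planned as a log-rank test with a Kaplan-Meier plot (Protocol 7.7.2, SAP 3.2.4), so dropping logistic regression changed nothing for it.

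**The tables may show more.** Layouts are in a separate mock-up document (SAP 3.6) that is not available here. The point concerns what the SAP text commits to.

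**The stakes are limited.** The affected endpoints are secondary or exploratory, in an unpowered trial that was stopped early, and both composites keep their difference CI. That lowers the importance of the point, but the change costs very little.

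**Conclusion.** The point holds in a limited form. For X-ray improvement, NIAID progression and improvement, Day 7 RT-PCR negativity and CRP normalization, the SAP text plans no between-arm estimate with a CI, and for RT-PCR no interval at all. At about 22 per arm, equal mid-range response rates leave differences of roughly 27 points either way compatible with the data. By domain, at an assumed 11 per arm, the figure is about 36 points. CRP is analysed only in subjects above the upper limit of normal at baseline, so its denominators cannot be larger and are probably smaller.

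These sizes rest on 1:1 allocation having held, on illustrative counts, and on unstratified intervals. The conclusion that an interval on the effect is missing rests on none of them. The documents do not show that SAP 3.4.1 alone created the gap, or that the planned output would conceal imprecision for X-ray, NIAID and CRP. The primary and all-cause composites are outside the point.

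**What to change.** In SAP 3.2.4 and 3.2.6, for each of the five responder endpoints:

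- Report the pooled risk difference, stratified by domain with Mantel-Haenszel weights, with a score-based 95% CI (stratified Newcombe or Miettinen-Nurminen). Name one method in advance.
- Report the unstratified score-based CI within each domain.
- Add per-arm Clopper-Pearson CIs for RT-PCR negativity, as the other endpoints already have.
- State that the interval is the main result and that it need not agree with Fisher's test at the margin. For example, 18/22 v 11/22 gives p = 0.055 with Newcombe +32 points (+4 to +54).

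A separate, optional addition, not linked to logistic regression, is a difference in restricted mean time to fever resolution with a 95% CI. A domain-stratified hazard ratio depends on event counts within strata and may be unstable in the febrile subset of 44 subjects.

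The cost is SAP wording, a few lines of code and a few more table rows, with no new data. The intervals will be wide, which reflects what the trial can show. If the data are already unblinded, the additions should be labelled post hoc.
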